5.3 Re-Treatment Criteria

A new cycle of treatment with PD 0332991 may begin only if:

- ANC \geq 1,000/mcL.
- Platelets count \geq 50,000/mcL.
- Non-hematologic toxicities have returned to baseline or no greater than grade 1 (or no greater than grade 2 if not considered a safety risk for the patient (at the investigator's discretion)).

If these conditions are not met, treatment with PD 0332991 must be delayed by one week. If, after a one-week delay, all toxicities have recovered within the limits described above, treatment with PD 0332991 can be resumed.

If the patient has not recovered after 2 weeks (including the scheduled 1-week off treatment period within a cycle), treatment with PD 0332991 will be permanently discontinued.

5.4 Dose Escalation Schema for Phase I

Dose Escalation Schedule (for the Phase I portion)		
Dose Level	PD 0332991 Dose*	Cetuximab Dose
Level -1	75 mg	Loading dose: 400 mg/m ²
Level 1 (Starting Dose)	100 mg	Weekly thereafter: 250 mg/m ² for
Level 2	125 mg	the duration of study participation

* PD 0332991 is administered on Days 1 through 21 of each 28-day cycle.

Dose escalation will not occur until all patients in the cohort have completed the first cycle and the Principal Investigator has been able to review all toxicities.

5.5 Definition of MTD, DLT, Dose Escalation Criteria, and Toxicity, Response, and DLT Evaluations for Phase I

5.5.1 Definition of Maximum Tolerated Dose (MTD)

The maximum tolerated dose (MTD) is defined as the dose level immediately below the dose level at which 2 patients of a cohort (of 2 to 6 patients) experience dose-limiting toxicity during the first cycle. Dose escalations will proceed until the MTD has been reached.

5.5.2 Dose Limiting Toxicities (DLTs)

Hematologic DLT is defined as any of the following that occur during the first cycle that are attributed as possibly, probably, or definitely related to the study treatment:

- grade 4 neutropenia ≥ 7 day duration
- grade 4 infection with grade 3 or 4 neutropenia
- grade 4 thrombocytopenia associated with life-threatening bleeding
- treatment held for > 14 days due to hematologic toxicity
- febrile neutropenia of any duration with temperature ≥ 38.5 °C

Non-hematologic DLT is defined as any possibly, probably, or definitely related grade 3 or grade 4 non-hematologic toxicity that occurs during the first cycle with the following specific exceptions:

- suboptimally treated grade 3 or 4 nausea, vomiting, diarrhea, anorexia, or lymphopenia
- grade 3 metabolic abnormalities (specifically limited to potassium, magnesium and calcium)
- any hypersensitivity / infusion reaction or acneiform rash due to cetuximab
- treatment held for > 14 days due to non-hematologic toxicity

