5.5.4 Toxicity, Response, and DLT Evaluations

All patients who receive any study treatment are evaluable for toxicity. Patients are evaluated from first receiving study treatment until a 30-day follow up after the conclusion of treatment or death.

All patients are evaluable for disease response unless they come off study due to treatment related adverse events(s) prior to completion of Cycle 2 and have not had any disease assessment.

A patient is evaluable for DLT assessment only during Cycle 1 of treatment and only if enrolled in phase I of the trial. If the patient is not able to be treated on Day 1 of Cycle 2, then s/he is still considered in Cycle 1 active treatment and can experience a DLT. Once the patient has been treated in Cycle 2, s/he will no longer be evaluated for DLTs in all subsequent cycles.

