6.0 DOSE DELAYS/DOSE MODIFICATIONS

6.1 Dose Modifications for PD 0332991

Patients will be monitored for toxicity and the dose of PD 0332991 may be adjusted as indicated in the table below. Dose reduction by 1, and if possible, 2 dose levels will be allowed depending on the type and severity of toxicity encountered. Patients requiring more than 2 dose reductions will be discontinued from the study.

Recommended dose reductions for PD 0332991 are to decrease the current dose by 25 mg. The lowest dose available is 75 mg. Doses may be held as needed for toxicity resolution during a cycle. Doses omitted for toxicity are not replaced or restored within the same cycle (meaning that the cycle remains 28 days regardless of the number of doses of taken).

If a patient experiences a toxicity which has not resolved to grade 2 or lower within two weeks (inclusive of the scheduled off-week), treatment with PD 0332991 should be

permanently discontinued.

PD 0332991 Dose Modifications Based on Worst Treatment-Related Toxicity in the Previous Cycle

Worst Toxicity During Previous Cycle	New Dose Level
Grade 4 neutropenia	Decrease by one dose level
Grade 4 thrombocytopenia	Decrease by one dose level
Grade 3 neutropenia associated with a documented infection or fever ≥ 38.5 °C	Decrease by one dose level
Grade ≥ 3 non-hematologic toxicity (includes nausea, vomiting, diarrhea, and hypertension only if persisting despite maximal medical treatment)	Decrease by one dose level
Delay by > 1 week in receiving the next scheduled dose due to persisting treatment-related toxicities	If recovery occurs within 2 weeks, continue and decrease by one dose level
Inability to deliver at least 80% of the planned dose of PD 0332991 due to adverse events possibly related to study treatment	Decrease by one dose level

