6.2.2 Gastrointestinal Adverse Effects

Antiemetic agents may be administered prior to the administration of cetuximab. Diarrhea will be treated symptomatically with antidiarrheal agents. Should GI toxicity become severe enough to require hospitalization or outpatient IV fluid replacement, all treatment should be discontinued temporarily until the patient's condition improves.

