6.2.6 Pulmonary Adverse Effects

In the event of acute onset (grade ≥ 2) or worsening pulmonary symptoms which are not thought to be related to underlying cancer, cetuximab therapy should be interrupted and a prompt investigation of these symptoms should occur. Cetuximab retreatment should not occur until these symptoms have resolved to grade 1. If interstitial lung disease is confirmed, cetuximab should be discontinued and the patient should be treated appropriately.

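### Section 5.5.2 lists a treatment hold of more than 14 days for non-hematologic toxicity as an exception to DLT, although the matching hematologic hold is a DLT

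*Combined protocol and SAP*

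**What the plan says.** Section 5.5.2 defines DLT through two lists with opposite logic.

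- **Hematologic list.** Each bullet is a DLT if it occurs in Cycle 1 and is at least possibly related. One bullet is "treatment held for > 14 days due to hematologic toxicity".
- **Non-hematologic definition.** Any related grade 3 or 4 toxicity counts "that occurs during the first cycle with the following specific exceptions". The first three exceptions are kinds of event: certain gastrointestinal events, anorexia and lymphopenia that were not optimally treated; grade 3 abnormalities of potassium, magnesium or calcium; and cetuximab infusion or hypersensitivity reactions and acneiform rash. The fourth is "treatment held for > 14 days due to non-hematologic toxicity".

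Four other sections bear on how the bullet works. Section 5.5.4 keeps a patient who cannot start Cycle 2 on time in the DLT window: "then s/he is still considered in Cycle 1 active treatment and can experience a DLT". Section 5.3 permanently stops PD 0332991 when recovery has not occurred after two weeks, counting the scheduled week off. Section 6.1 does the same: "If a patient experiences a toxicity which has not resolved to grade 2 or lower within two weeks". Section 5.6 records that phase I ended at 125 mg with no MTD found.

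**The concern.** The exception runs backwards. A long interruption is normally evidence that a toxicity limits dosing, yet here it is the long interruption that takes the event out of the count. The hematologic list treats the same consequence the opposite way, and no section gives a reason for the difference or restores the criterion elsewhere.

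The DLT count is the only input to the MTD, which is the phase I primary objective, and the 125 mg phase II dose was carried forward on that result. Phase I is complete, so what is at stake now is whether its result is reported against a correct definition. A reader of the protocol cannot tell whether investigators applied the bullet as printed or as presumably meant.

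**Working it through.** No sample-size or power figure is involved, so the check is one of logic.

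**Step 1. Classify related Cycle 1 events to which none of the first three exceptions applies.**

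| Event | Literal reading | Softer reading (a hold is not a toxicity) | After correction |
|---|---|---|---|
| Hematologic toxicity, hold > 14 days | DLT | DLT | DLT |
| Grade 3-4 non-hematologic, hold of 14 days or less | DLT | DLT | DLT |
| Grade 3-4 non-hematologic, hold > 14 days | not a DLT | DLT | DLT |
| Lower-grade non-hematologic, hold > 14 days | not a DLT | not a DLT | DLT |

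The literal reading loses the last two rows and the softer reading loses the last one. Neither adds a DLT anywhere, so the direction is fixed: the printed count is at or below the corrected one.

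**Step 2. Is misplacement the likely explanation?** The wording matches the hematologic bullet except for the prefix. The other three exceptions are types of event, whereas this one is a consequence. Section 5.5.4 extends the DLT window for a delayed Cycle 2, which sits oddly with an exemption for long delays. This is inference, but the signs agree.

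**Step 3. Which holds could be affected?** Sections 5.3 and 6.1 end PD 0332991 at about two weeks, so few PD 0332991 holds can run beyond 14 days. But Section 5.5.2 says treatment without naming a drug, and two non-hematologic holds carry no time limit of their own. For severe GI toxicity, Section 6.2.2 says "all treatment should be discontinued temporarily until" the patient improves. For pulmonary symptoms, Section 6.2.6 says cetuximab "retreatment should not occur until these symptoms have resolved to grade 1". Section 6.1 still caps the PD 0332991 part of a GI hold if the toxicity stays above grade 2. What remains is mainly long cetuximab holds for GI or pulmonary events.

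**Step 4. What would an uncounted event do to the result?** Let *c* be the DLTs counted at 125 mg and *u* the holds left out by the bullet, so the corrected total is *t* = *c* + *u*. The documents give neither number.

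| *t* at 125 mg | Section 5.5.1 (MTD is the level below the one with 2 DLTs) | Section 15 table, cohort 2 |
|---|---|---|
| 0 | no MTD found | MTD not reached |
| 1 | no MTD found still stands | three more patients at dose 2, or dose 2 named the MTD |
| 2 | MTD is 100 mg | dose 1 (100 mg) is the MTD |

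One event therefore leaves the dose at 125 mg under both rules, and changes the stated conclusion only under Section 15. If the three added patients brought a second DLT, the row for 2 would apply. The dose moves only if the corrected total at 125 mg reaches two, for example 0 + 2 or 1 + 1. An uncounted hold at 100 mg would also have mattered at the time: in the Section 15 table, one DLT there means three more patients and two mean de-escalation.

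**The case against.** The strongest reply is that the base rule counts toxicities and a hold is not a toxicity. On that view the bullet excuses nothing at grade 3-4, and no investigator would count an event and then remove it on day 15. This is a fair reading and may be how the trial was run. It does not rescue the text: a lower-grade toxicity that stops treatment for more than 14 days is then a DLT if hematologic and not if non-hematologic, with no reason given.

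A second reply is that the list was read from a PDF and a lost indent or separate lead-in cannot be fully excluded. That is true, but nothing in the text points to one.

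A third is that little is left to protect. Phase I is finished, the Principal Investigator reviews all toxicities before escalation (Section 5.4), and the phase II toxicity boundaries for Arms 1 and 2 use grade 3-4 toxicity rather than the DLT definition. This limits the severity. The review before escalation is not a cure, though, because the reviewer applies the definition in Section 5.5.2.

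A reader might also infer that Sections 5.3, 6.1 and 5.5.4 contradict the bullet. They do not. None of them says whether a hold counts as a DLT; they only make the literal reading clinically implausible.

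**Conclusion.** The DLT definition is wrong as written, at low severity. The bullet is most likely a DLT criterion in the wrong list, and it can only lower the DLT count or leave it unchanged.

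Two stronger conclusions are tempting and not supported. The first is that 125 mg was chosen in error. The documents report no phase I DLT counts and no prolonged holds, so no effect on any patient or on the dose is shown. The second is that a single uncounted event would overturn the finding of no MTD. That follows only from the Section 15 rows; Section 5.5.1 needs two DLTs at a level.

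I give no probability that the result would change. It would need the true DLT rate and the share of DLT patients whose only DLT was an excused hold, and neither is in the documents. The effect is probably small, because the two-week stops leave few PD 0332991 holds within reach and because two DLTs at 125 mg are needed to move the dose.

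**What to change.** 1. Remove the fourth bullet from the exceptions and state it as a DLT criterion in the same terms as the hematologic one: *treatment held for more than 14 days because of related non-hematologic toxicity*. Keep the exception for cetuximab hypersensitivity or infusion reactions and acneiform rash in force.
2. Do not add permanent discontinuation as a DLT. The hematologic list has no such item. The two-week stop includes the scheduled week off, so it could trigger about one week past schedule (2 - 1 = 1 week). That would be stricter than the hematologic rule and would replace one asymmetry with another.
3. Check the phase I records, at most 12 by Section 15, for such Cycle 1 holds of either drug, including a delayed start of Cycle 2. Report grade 3-4 and lower-grade holds separately: the first become DLTs once the exception is removed, the second only under the restated criterion.
4. If any exist, re-apply the MTD rules, say whether Section 5.5.1 or Section 15 is used, and confirm or restate the phase I conclusion. If none exist, say so in one sentence of the report.

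The cost is one bullet moved and one item checked in at most 12 records. No treatment changes, and re-adjudication is needed only if an event is found.

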5.5.3 Dose Escalation Criteria

Dose escalations will proceed as follows after the occurrence of dose-limiting toxicity (DLT):

Number of Patients with DLT at a Given Dose Level	Escalation Decision Rule
0 out of 3	Enter 3 patients at the next dose level.
≥ 2	Dose escalation will be stopped. Three (3) additional patients will be entered at the next lowest dose level if only 3 patients were treated previously at that dose.
1 out of 3	Enter at least 3 more patients at this dose level. If 0 of these 3 patients experience DLT, proceed to the next dose level. If 1 or more of this group suffer DLT, then dose escalation is stopped. Three (3) additional patients will be entered at the next lowest dose level if only 3 patients were treated previously at that dose.
≤ 1 out of 6 at highest dose level below the maximally administered dose	This is generally the recommended phase 2 dose. At least 6 patients must be entered at the recommended phase 2 dose.

5.5.4 Toxicity, Response, and DLT Evaluations

All patients who receive any study treatment are evaluable for toxicity. Patients are evaluated from first receiving study treatment until a 30-day follow up after the conclusion of treatment or death.

All patients are evaluable for disease response unless they come off study due to treatment related adverse events(s) prior to completion of Cycle 2 and have not had any disease assessment.

A patient is evaluable for DLT assessment only during Cycle 1 of treatment and only if enrolled in phase I of the trial. If the patient is not able to be treated on Day 1 of Cycle 2, then s/he is still considered in Cycle 1 active treatment and can experience a DLT. Once the patient has been treated in Cycle 2, s/he will no longer be evaluated for DLTs in all subsequent cycles.

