5.6 Dosing for Phase II

Dosing for phase II will be administered as per Section 5.2. Dose of PD 0332991 will be 125 mg, which was the highest dose given in phase I (no MTD found). Thirty patients will

be enrolled to Arm 1 of phase II, 30 patients will be enrolled to Arm 2 of phase II, and 24 patients will be enrolled to Arm 3 of phase II. Enrollment for all arms may take place concurrently.

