15.0 STATISTICAL CONSIDERATIONS

This trial consists of an open-label phase I study, where the MTD and DLT of the combination of PD 0332991 will be determined, followed by a phase II study where patients with incurable HPV-unrelated SCCHN will be treated with PD 0332991 and cetuximab. The phase I portion of the study will adopt a 3 + 3 design and at most 12 patients will be needed in this group.

Dose escalations and de-escalations will proceed as follows after the occurrence of dose-limiting toxicity (DLT):

[figure not shown]
Cohort	# DLTs	Escalation Decision Rule
1	0	Escalate to dose 2.
	1	Enter 3 additional patients at dose 1.
	2	De-escalate to dose -1.
2	0	Conclude that the MTD has not yet been reached.
	1	Enter 3 additional patients at dose 2 if 0 in cohorts 1 and 2. Identify dose 2 as the MTD if 1 in cohorts 1 and 2.
	2	Conclude that dose 1 is the MTD.

For the phase II Arm 1 portion, based upon currently available data for cetuximab alone in platinum-resistant incurable SCCHN³⁷, an overall tumor response rate (CR + PR) of 13% or lower would be unacceptable and an overall tumor response rate of 26% or higher of clinical interest. A total of 30 eligible and evaluable patients will be accrued to the phase II portion of the study, and if 4 or more patients' tumors respond, the therapy will be accepted for further investigation. The design is based on Thall P and Sung H-G³⁸.

Assumes 13% response with standard treatment, response rate increase of 13% (26% response rate with experimental treatment), expected (grade 3 or 4) toxicity rate of 46% with standard, 0% allowable increase with experimental treatment.

Stop for poor response if:		Stop for excess (grade 3 or 4) toxicity if:	
# Patients is:	# Responses is ≤:	# cases of toxicity is ≥:	In 1 st # patients
3	0		
4	0	4	4
5	0	5	5
6	0	5	6
7	0	6	7
8	0	7	8
9	0	7	9
10	0	8	10
11	0	8	11
12	1	9	12
13	1	10	13

14	1	10	14
15	1	11	15
16	1	11	16
17	1	12	17
18	2	13	18
19	2	13	19
20	2	14	20
21	2	14	21
22	2	15	22
23	2	15	23
24	3	16	24
25	3	17	25
26	3	17	26
27	3	18	27
28	3	18	28
29	3	19	29
30	3	19	30

For the phase II arm 2 portion, the tumor response rate to any agent in patients with cetuximab-resistant incurable SCCHN is unknown but it is expected to be < 13%. An overall tumor response

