rate (CR+PR) of 13% or lower would be unacceptable and an overall tumor response rate of 26% or higher would be of clinical interest. A total of 30 eligible and evaluable patients will be accrued to the phase II arm 2 portion of the study, and if 4 or more patients' tumors respond, the therapy will be accepted for further investigation. The design is based on Thall P and Sung H-G³⁸. The table and figure above also apply to phase II Arm 2.

For phase II Arm 3 portion, an overall tumor response rate (CR + PR) of 5% or lower would be unacceptable and an overall tumor response rate of 20% or higher of clinical interest. A total of 24 eligible and evaluable patients will be accrued to this arm. One or more tumor responses in the first 18 patients are required to continue enrollment. Two or more tumor responses in the first 24 patients are required to accept the alternative hypothesis. The design has probability = .74 of early stopping after the first cohort of 18 patients if the true response rate is 5% or less. The cumulative probability of completing the study (enrolling 24 patients) is 0.70 if the true response rate is 20% or greater. The design is based on Thall P and Sung H-G³⁸.

Number of patients	Cumulative probability of early stopping if response rate = 5% (null hypothesis)	Cumulative probability of early stopping if response rate = 20% (minimum alternative hypothesis)	Cumulative probability of continuing to end of study if response rate = 20% (minimum alternative hypothesis)
1	0	0	0
18	0.7436	0.2858	.7142
24	0.8335	0.2953	.7047

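### The phase II response rate leaves out patients who come off study early for related toxicity with no disease assessment, an exclusion that can raise the primary endpoint but never lower it

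*Combined protocol and SAP*

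**What the plan says.** The phase II primary endpoint in each arm is ORR (CR+PR) by RECIST (Section 2.1). Section 15.0 sets the sizes. For Arm 1: "A total of 30 eligible and evaluable patients will be accrued to the phase II portion of the study". Arm 2 has the same number on the same basis. For Arm 3: "A total of 24 eligible and evaluable patients will be accrued to this arm". Section 15.0 does not define evaluable.

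The only definition of response evaluability is in 5.5.4: "All patients are evaluable for disease response unless they come off study due to treatment related adverse events(s) prior to completion of Cycle 2". The sentence then adds that the patient must also have had no disease assessment. The parent heading, 5.5, ends "Toxicity, Response, and DLT Evaluations for Phase I". Within 5.5.4, however, only the DLT paragraph is confined to patients "only if enrolled in phase I of the trial".

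Toxicity has a wider base: "All patients who receive any study treatment are evaluable for toxicity". Section 5.6 gives the same counts as enrolled rather than evaluable, for example "30 patients will be enrolled to Arm 2 of phase II". No section says whether an inevaluable patient is replaced or counted as a non-responder, and none plans an all-treated ORR.

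**The concern.** The rule removes one group selectively. Patients who leave early because of progression, an unrelated event or withdrawal stay in the denominator. Patients who leave for an event judged related to treatment, with no assessment, do not. In an open-label trial, that judgement then decides who counts towards the primary endpoint.

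Under 12.4.3 a response needs both measurement and confirmation, so an excluded patient could never have been a responder. The ORR is compared with a fixed 13% (Arms 1 and 2) or 5% (Arm 3), so no control arm shares the bias. The documents do not say whether the 13% itself came from all treated or only from evaluable patients.

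The interim rules are exposed too. In the Section 15.0 table, 1 response in 12 stops the arm. If one of those 12 is excluded, the count reads 1 in 11 and the arm continues. Because toxicity is counted in all treated patients, the two halves of that table can run on different patients.

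**Working it through.** **The plan's own figures.** Section 15.0 gives no error rates for Arms 1 and 2. For Arm 3 it gives a .74 chance of stopping after 18 patients at a 5% response rate. The rule as written gives 0.95^18 = 0.397, so that figure does not reproduce. This is a separate matter and does not bear on the present point. The Arm 3 figures below use the rule as written.

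**Direction.** With r responders among n treated and m excluded non-responders, r/(n−m) ≥ r/n, strictly so when r and m are at least 1. Example: 4/30 = 13.3%, but with 3 excluded 4/27 = 14.8%.

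**Inputs.**
- Arms 1 and 2 response boundary (Section 15.0): stop at 0 responses for n = 3–11, ≤1 for 12–17, ≤2 for 18–23, ≤3 for 24–30. The final count rule is 4 or more of 30.
- Arm 3 (Section 15.0): at least 1 response in 18, then at least 2 in 24.
- Exclusion share d: not in the documents. Assumed to be 10%, 20% or 30% of the "expected (grade 3 or 4) toxicity rate of 46% with standard", so d = 0.46 × 0.10, 0.20, 0.30 = 4.6%, 9.2%, 13.8%. Per 30 treated that is 1.4, 2.8 or 4.1 patients. The 46% is any grade 3–4 toxicity, not early exit, so it serves only to scale the range.

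**Method.** If the rate among all treated patients is p and none of the excluded respond, the rate among evaluable patients is p/(1−d). At p = 13% this is 13.6%, 14.3% or 15.1%. These rates go into an exact binomial tail or an exact patient-by-patient recursion over the boundary. The toxicity boundary is ignored throughout.

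**Chance of passing at the unacceptable rate.**

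| Rule | d = 0 | 4.6% | 9.2% | 13.8% |
|---|---|---|---|---|
| Arms 1/2, sequential boundary, true 13% | 16.5% | 18.4% | 20.4% | 22.8% |
| Arms 1/2, 4 of 30 alone, replaced | 55.9% | 59.9% | 64.0% | 68.3% |
| Arms 1/2, 4 of 30 alone, not replaced | 55.9% | 55.9% | 55.9% | 55.9% |
| Arm 3, true 5%, replaced | 32.6% | 34.7% | 37.0% | 39.5% |
| Arm 3, true 5%, not replaced | 32.6% | 33.0% | 33.3% | 33.5% |

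Replacement hardly affects the first row. The boundary stays at 3 from the 24th evaluable patient on, so passing is settled there, and up to 6 exclusions among 30 change nothing. A recursion over 30 treated patients, each excluded with probability d, gives the same figures to within about 0.1 point.

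The 4-of-30 rule is a count of responders. Without replacement, excluding non-responders leaves that count unchanged. In Arm 3 without replacement, the pass chance cannot exceed P(2 or more of 24) = 33.9%.

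**If patients are replaced,** reaching 30 evaluable takes 30/(1−d) = 31.4, 33.0 or 34.8 treated on average, while the toxicity table ends at 30.

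**Effect of counting everyone, Arms 1/2 sequential boundary.**
- If 26% is the rate among evaluable patients, the all-treated rate is 0.26(1−d) = 24.8%, 23.6% or 22.4%. The pass chance falls from 54.0% to 51.1%, 48.1% or 44.8%.
- If 26% is the rate among all treated patients, the present rule passes 56.9%, 59.8% or 62.9%. Counting everyone gives 54.0%.

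**The case against.** **The rule may not apply to phase II.** Its parent heading names phase I, and Section 15.0 never refers to 5.5.4. Applying it is an inference, but a sound one: the phase I limit in the DLT paragraph would be redundant if the whole subsection were phase I only. If the rule does not apply, evaluable has no definition for the primary endpoint, and the text needs repair anyway.

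**The group is narrow.** This stands. Early exit, related toxicity and no disease assessment must all coincide. An assessment need not be a CT, since superficial lesions can be measured by caliper (12.3). Section 11.0 asks for a tumor form at the end of treatment, and 5.9 keeps patients who stop early in follow-up. Phase I reached 125 mg with no MTD found (5.6). Against this, the first on-study CT is due only at 8 weeks, the calendar lists none at end of treatment or in follow-up, and follow-up may be by telephone or record review.

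**A reader might infer that the drug-stopping rules feed this group:** non-recovery after 2 weeks (5.3), grade 4 QTc (6.1.1) or a grade 4 cetuximab reaction (6.2.3). The text does not support that. Each stops one drug and does not say the patient comes off study. Section 5.10 does foresee removal from study for adverse events, but gives no frequency.

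**A reader might also infer that early toxicity can only help the trial succeed.** That goes too far. The toxicity boundary counts all treated patients, and toxicity may lower response in those who stay on. The one-way effect belongs to the exclusion alone.

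**Conclusion.** The point holds for the exclusion rule. As written, the phase II ORR can be raised, and never lowered, by leaving out patients who come off study early for related toxicity with no disease assessment. The text does not settle whether they are replaced.

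Under an assumed exclusion of 4.6% to 13.8%, the chance of passing the Arm 1/2 response boundary at a true 13% rises by about 2 to 6 points (18.4 − 16.5 = 1.9; 22.8 − 16.5 = 6.3), whether or not patients are replaced. A reader might take 68.3% for 4 of 30, or 39.5% for Arm 3, as the plan's false-pass rate. The documents do not support that: both need replacement and the highest assumed exclusion, and the 4-of-30 figure also ignores the interim stops. Without replacement the 4-of-30 figure does not move, and Arm 3 rises by about 1 point at most.

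The direction is certain and the size is not. With no such exits, the effect is zero.

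**What to change.** In Section 15.0, for all three arms:
- Define the primary ORR on every eligible patient who received any study treatment (30, 30 and 24, which matches 5.6).
- Count a patient with no post-baseline disease assessment as a non-responder, whatever the reason for leaving, and do not replace that patient.
- Read the response and toxicity boundaries on the same sequence of patients.

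In 5.5.4, state that for phase II the present exclusion defines only a supportive, evaluable-only ORR.

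The cost is a text amendment. Boundaries and planned enrolment stay as they are, and no extra scan is needed, because a missing assessment is handled in the analysis. The price is a less favourable ORR: the pass chance in Arms 1 and 2 falls by about 3 to 9 points over the assumed range, whichever population the 26% is taken to describe.
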